Semi-structured qualitative interviews will proceed with participants who give verbal consent. Due to the variable nature of response and participant engagement interviews are estimated to last between 30 minutes and 60 minutes. The interview guide includes planned questions that will be asked to every participant. Due to the nature of semi-structured interviews, we may ask appropriate follow-up questions or ask participants to elaborate upon statements made. Study questions include appropriate warnings about the sensitivity of questions, where participants may be asked directly about negative experiences with healthcare or to elaborate on negative study experiences. As appropriate, participants will be reminded that they can take breaks, skip questions they are uncomfortable answering, or stop the interview at any time. Interviews will be conducted primarily by [name] as part of a Master's of Genetic Counseling research requirement, with [name] and [name] to supplement interviews as needed.

Participants who are interviewed will receive a \$40 Visa gift card as compensation for their time. Visa gift cards will be sent to interviewed participants via email. Individuals who decide to end the interview early will still be compensated with the same gift card.

Consent to interview and the interview itself will be recorded on secure Microsoft Teams software, which is the preferred secure software of VUMC and transcribed using auto transcription that comes pre-installed with Microsoft Teams. Recordings and raw transcripts will be maintained on a secure study server within Microsoft OneDrive, with access only available to approved study personnel. These transcripts will then be supplemented with manual revisions based on raw recordings (to catch

autotranscription errors) and manual redaction of any identifying information – including about individuals other than the participant. Because of the sensitive sociopolitical climate for TGSD persons, transgender team members ([name] and [name]) will review redacted transcripts for potentially sensitive data that falls outside the scope of data that is traditionally considered identifiable, and may choose to apply stricter data censoring at this time. Deidentified transcripts will be uploaded to Dedoose, a cloud-based coding software used to analyze qualitative research.

6. Reporting of Adverse Events or Unanticipated Problems involving Risk to Participants or Others

All researchers will report all events that are serious, unexpected, and study-related to the PI by phone, fax or email within 24 hours of becoming aware of the event. We will promptly report to the IRB any participant complaints about the conduct of any element of the study or concerns about potential harms, including copies of any written communication with the participant addressing those concerns. Further, all conversations with participants that indicate a level of concern about a study component - even if not a complaint - will be documented and distribution of any participant education materials in response to such queries will be documented in the participant's research (REDCap) record for the primary study (FOREST). There is the possibility of identifying someone who received inappropriate clinical recommendations from MeTree based on their response to the sex question in MeTree, which is used in assessing clinical risk. If someone like this is identified, this would be reported under the FOREST study protocol, and a new MeTree risk report would be generated.

7. Study Withdrawal/Discontinuation

Withdrawing participation from interview substudy

We will continue to utilize the participant interview data in analyses unless the participant asks for the data to be withdrawn. If a participant requests that data be withdrawn, raw transcripts and recordings will be deleted, as well as any data derived from these that are present in Dedoose or analyses. Participants who request that interview data be withdrawn will be notated as actively withdrawn and that they requested interview data removal in the tracking database, so that we can maintain information about participants. Subjects who wish to withdraw from the main study will be withdrawn from FOREST under the main study protocol.

Active Declining Participants

As noted above, participants can ask to stop the interview at the time, for any reason. If participants wish to stop the interview permanently and not reschedule for a follow-up, they will be considered withdrawn. Withdrawn participants will follow the withdrawing participation procedure above.

Non-responders (Passive Decline)

Potential interviewees who agree to interview, but fail to schedule and are unable to be reached or fail to attend their interview and are unable to be rescheduled will be considered passive decliners. Similarly, if a participant phone call is lost during interview and they are unable to be reached again to reschedule the rest of the interview, they will be considered passively withdrawn and will follow the procedure above regarding the interview data that was collected until the dropped call.

Surveys of declination or withdrawal

Participants that ask to stop the interview, request or withdraw from the study will be asked why they are making this choice. This information will be tracked in the tracking database for the main FOREST study.

Deceased participants

The study will utilize the data of deceased participants even if they pass before the conclusion of the study.

8. Analytic Considerations

[name], [name], and [name] will develop a qualitative codebook using inductive and deductive techniques. This codebook will be refined with input from the rest of the FOREST study team and [name] thesis committee. Dedoose will be used for coding, with [name] will act as a dual coder for [name]. [name] or another member of [name] committee will serve as tiebreaker. Themes will then be identified and findings synthesized.

9. Privacy

As noted above every effort will be made to remove identifying information from study transcripts and participant summaries. There is no intervention in this substudy of FOREST. However, there is the possibility that a participant may report emotional distress when recounting experiences with the FOREST study or previous personal experiences. In the case of this occurring, we will provide participants appropriate numbers to VUMC mental health resources. This referral resource will include the VUMC psychology/psychiatry phone number, helplines, and other helpful resources. Should this occur, it would also be reported to the IRB. All interview data will be deidentified before coding in Dedoose, and only de-identified data will be shared. All identifiable data will be stored on secure servers and only accessible to a minimum subset of study personnel. Given the sensitive nature of participant gender identities in the current societal climate, additional efforts may be undertaken beyond typical requirements under HIPAA to further obscure participant identities or sensitive information. Two key personnel on the primary FOREST study, [name] and [name], who both have transgender identities and are connected to the Nashville transgender community, will guide whether additional data obfuscation beyond HIPAA is necessary to protect participants.

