The practice of genetic medicine is changing as genetic discoveries are translated into new tests for an increasing number of health indications. In fact, the prevalence of high-risk individuals who are at risk for hereditary cancer has been rising due to new testing strategies. This has placed enormous pressure on the hospitals and clinics providing care for high-risk patients. Coupled with the healthcare system's need for greater efficiency, the traditional genetic clinic-based practice has become untenable. Barriers and challenges include low numbers of trained genetic workforce, lack of integrated FHH platforms for patients and physicians, and long wait times for available clinic appointments. Further, while cancer syndromes are seen across all groups, gaps in care exist as underserved populations are often not recognized and referred for care.

MeTree is a computer platform that has been developed by researchers at Duke University that electronically collects FHH information for hereditary cancer syndromes and other health conditions directly from the patient. MeTree then calculates hereditary cancer risks for the patient and creates a personalized patient report and evidence-based clinical decision support for the provider. In previous studies, MeTree demonstrated improvements in the identification of those at risk and highlighted ongoing challenges particularly around undergoing genetic counseling and testing, and awareness of risk. Co-investigators from Duke/MeTree collaborate on this grant.

2. Rationale and Specific Aims

SA1. Deploy a care delivery model that will facilitate systematic risk assessment for hereditary cancers in diverse clinical environments.

- Up to 3,500 participants will be enrolled and complete the MeTree FHH risk assessment
- Deploy in 2 academic medical centers; Vanderbilt University Medical Center (VUMC) and Meharry Medical College (MMC)
- Assess participants perceptions using online survey and qualitative semi-structured interviews

SA2. Improve access to genetic healthcare providers for participants at risk for hereditary cancer syndromes.

- 300 high risk participants in the VUMC Hereditary Cancer Clinic will be enrolled
- Extend clinic capacity by lessening the need for in-clinic family history collection and basic counseling
- Expand reach of clinic by using telephone and video genetic counseling; referral to specialists

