If a patient clicks, I'm Interested, the REDCap Participant Updater Module will create a record in the study database that includes patient MRN and the enrollment status of Interested. Once the Updater Module creates a new record, it will trigger REDCap to fetch the email address to facilitate sending the follow-up email from REDCap, which will include more information about the study and a link to the survey.

[name]
U01-CA232829-01A1
FOREST

If a patient clicks, No, Thank You, the REDCap Participant Updater Module will create a record in the study database that includes patient MRN and the enrollment status of Not Interested. This will prevent any further communication to the patient about this study.

Once the eligible participant enters the REDCap study pre-screen, they will be able to complete the eligibility survey, electronic consent, and pre-MeTree survey. At the end of the pre-MeTree survey, participants will be given a link to the MeTree platform to begin the questionnaire. At any time, they can leave MeTree and re-enter by using the link from the REDCap message or by the link in their MHAV portal. Participants will receive a \$10 gift card for completing the eligibility, eConsent, and pre-MeTree surveys.

After completing the eligibility, eConsent, and pre-MeTree surveys, participants will receive an email with the link to MeTree (**Appendix K**). Participants have three weeks to complete their MeTree questionnaire. After completing the questionnaire, participants will receive a report from MeTree. After receiving the report from MeTree, and once the study team has concluded the enrollment of the 3,500 participants, 300 “high risk” participants will be referred to the Hereditary Cancer Clinic to discuss their results with a Genetic Counselor. The consent will include information about this step to inform participants that they may be contacted for counseling.

*My Health at Vanderbilt (MHAV) language is used to describe the workflow at Vanderbilt.

5. Study Procedures

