Once data entry in MeTree is complete all participants will receive a personalized patient report within the platform outlining their familial and genetic risk status the included medical conditions according to current evidence-based guidelines. Participants' providers will be notified via one of several methods (email without PHI, EPIC messaging, or an alert) that their patient has a MeTree clinical decision support report available in the medical chart (accessible via a SMART link). Outside providers will receive an email or letter. The templates for these messages is located in Appendix I. The process to upload the MeTree report and provide accessibility to providers is approved by the Medical Forms Committee and the Center for Health Information Management (CHIM) Committee.

As previously stated, in Aim 2 participants who are identified as at high genetic risk (n=300) will be contacted by the study nurse (as part of their standard of care) to schedule a genetic counseling appointment (Appendix J, High risk patient email). The number and length of genetic counseling appointments will be recorded in order to evaluate the change in clinic capacity for those with a pre-recorded FHH in the MeTree platform as compared to routine patients who have not participated in the study and completed MeTree. The frequency of genetic testing and outcomes of the testing will also be recorded in REDCap from data collection in the Hereditary Cancer Clinic at VUMC.

[figure not shown]
To analyze the time saved by completing MeTree prior to a clinic visit, the study team will perform a retrospective review of control patients, selected by the study team, to assess the amount of time in clinic with the genetic counselors. This will be done through time stamps in eStar and chart review. Control patients will not be a part of the study, nor will their information be shared with anyone. The study team will only review for time spent in clinic versus the study participants' clinic visits.

Additionally, genetic counselors who see participants from this study will be surveyed to better understand their perspective of the use of MeTree. This portion of the study will be in a separate IRB.

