We will use a case-control design for statistically analyses. Cases are defined as the study participants who have completed the MeTree tool (intervention). We will utilize data from the Hereditary Cancer Clinic registry (IRB # 141203) to fine patients identified at risk of a hereditary cancer syndrome in the usual care (control) and intervention conditions. The control condition utilizes historical data from the participants prior to their enrollment date in FOREST to determine the number and proportion of participants who would be identifiable as at risk without the implementation of MeTree. We believe this is the most effective method to analyze the MeTree platform's effect on hereditary cancer testing and outcomes. Power calculations estimate a sample size of up to 3,500 (minimum of 3,000) is needed to produce statistically significant results.

In the graph below, the blue line represents 90% power to detect the primary endpoint with a p-value of 0.05, the green line, 85% power, and the red, 80% power. The x-axis represents how many participants are identified as being at high risk by MeTree.

In prior studies of primary care populations, on average 20% were newly found to be at high risk (had not previously identified). However, in order to accommodate differences in a population that has a proactive hereditary cancer clinic, we used a lower estimate of 10% for the power analyses. Thus at 10% risk identification and 95% power we estimated that we would need at a minimum 1,000 participants for a single site and 2,000 participants total to detect differences in identification at the 2 sites (Meharry and Vanderbilt). In addition, these participants flow into aim 2. Based on power analysis to detect an increase in clinic capacity, we need to have 150 high risk patients who complete MeTree in Aim 1 to see a genetic counselor in the hereditary cancer clinic at Vanderbilt. At a 10% identification rate and a 50% follow up rate (estimate based on literature review and the clinic's attendance rate), a minimum of 3,000 participants will need to complete MeTree in Aim 1. We are therefore enrolling 3,000-3,500 participants for this study.

Data elements considered for this analysis:

Primary Endpoint: Participant designated as high risk for cancer.

Assessment pre: chart review (any indicator prior to MeTree, not time-frame dependent)

Assessment post: MeTree report (measured when the report is generated, independent of amount of follow-up time)

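### Protocol Section 8 uses the 3,000 participants who must complete MeTree as the lower end of the enrolment range, with no allowance for non-completion, so the Aim 2 target of 150 seen needs 100% completion at 3,000 enrolled or 85.7% at 3,500

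*Protocol*

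**What the plan says.** Protocol Section 8 (Statistical Considerations) opens with an overall size: "Power calculations estimate a sample size of up to 3,500 (minimum of 3,000) is needed to produce statistically significant results". That sentence does not say whether the count is of people enrolled or people completing, although the same paragraph defines cases as participants who have finished the tool.

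The derivation comes later in Section 8. The Aim 2 requirement, for the Vanderbilt clinic, is this: "we need to have 150 high risk patients who complete MeTree in Aim 1 to see a genetic counselor in the hereditary cancer clinic". With 10% identified as high risk and 50% following up, the section concludes: "a minimum of 3,000 participants will need to complete MeTree in Aim 1. We are therefore enrolling 3,000-3,500 participants for this study". It explains that 10% was set below earlier experience in primary care, where "on average 20% were newly found to be at high risk".

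Other places that bear on the two counts:

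- Section 2, SA1, gives one number for both steps: "Up to 3,500 participants will be enrolled and complete the MeTree FHH risk assessment".
- Section 4 (Enrollment) times the referral of 300 high-risk participants to the point "once the study team has concluded the enrollment of the 3,500 participants". Section 5 repeats the 300: "participants who are identified as at high genetic risk (n=300) will be contacted by the study nurse".
- Section 5 has participants asked to fill in MeTree after they have enrolled, with reminders for Vanderbilt participants who do not access it.
- Section 7 allows removal of people who have not completed within 12 months of enrolling. It classes those who never complete as enrolled but excluded.
- Section 11, the subproject's inclusion criteria, acknowledges that some enrolled FOREST participants have not completed MeTree.
- The SAP (II.2, III.1, IV.2) makes completion of MeTree the primary outcome, reported as a number and percentage, and gives no expected value.

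**The concern.** A requirement for completers has become a minimum for enrolment with no completion rate in between. The two counts are equal only if everyone who enrols completes, and the plan does not expect that: it has reminders, a removal rule and an exclusion category for non-completers, and it measures completion as its primary outcome.

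The size of Aim 2 is at stake. The 150 is what the protocol's Aim 2 power analysis calls for, and these participants form the MeTree group in the SAP's Secondary Endpoint 2 (appointment length, with comparators selected 1:1). If enrolment stopped at the stated minimum, a team following Section 8 would believe the requirement was met when, at the section's own rates, it would be met only with no non-completion at all.

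**Working it through.** **Inputs.** From Protocol Section 8: 150 high-risk completers seen, 10% identification, 50% follow-up, 3,000 to 3,500 enrolled, and an Aim 1 minimum of 2,000 in total (1,000 per site). The completion rate c is in neither document; 70, 80 and 90% are used below as assumptions.

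**1. The plan's own figure.** Completers needed = 150 / (0.10 x 0.50) = 3,000. This reproduces the protocol and confirms that 3,000 counts completers.

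**2. Break-even completion.** Required c = 3,000 / enrolled.

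- At 3,000 enrolled: 3,000 / 3,000 = 100%.
- At 3,500 enrolled: 3,000 / 3,500 = 85.7%, so at most 14.3% may fail to complete.

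**3. Expected number seen.** Seen = enrolled x c x 0.10 x 0.50.

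| Assumed completion | Seen from 3,000 | Seen from 3,500 |
|---|---|---|
| 70% | 105 | 122.5 |
| 80% | 120 | 140 |
| 90% | 135 | 157.5 |

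The target is 150. These are expected values. Even with exactly 3,000 completers, the binomial chance of at least 150 seen (probability 0.05 each) is about 51%.

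**4. Sensitivity to the 10%.** Identification rate needed = 150 / (enrolled x c x 0.50).

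- At 3,500 enrolled: 150 / 1,400 = 10.7% at 80% completion; 150 / 1,225 = 12.2% at 70%.
- At 3,000 enrolled: 150 / 1,200 = 12.5% at 80%; 150 / 1,050 = 14.3% at 70%.
- At the 20% of prior studies, 150 / (0.20 x 0.50) = 1,500 completers are enough, which is 50% completion of 3,000.

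**5. Aim 1.** 2,000 / 3,000 = 66.7% and 2,000 / 3,500 = 57.1%. The Aim 1 total therefore survives completion well below 85.7%, provided each site reaches its 1,000.

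**6. What a shortfall would cost in power (illustration only).** The documents give no effect size, standard deviation or power for the 150. Suppose 150 per group gave 80% power at two-sided 0.05. Under a normal approximation with both groups shrinking together, power = Φ((1.960 + 0.842) x sqrt(n/150) - 1.960). That gives about 77% at n = 140, 72% at 122.5, 71% at 120 and 65% at 105.

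**The case against.** The strongest reply is that the 500 between 3,000 and 3,500 is the allowance, and that enrolling is shorthand for enrolling and completing, as SA1 words it. The paragraph that opens Section 8 also defines cases as completers, which supports reading its minimum as a completer count. The headroom is real and is credited above. But no passage calls it an allowance, it is a ceiling rather than a commitment, and it works only at 85.7% completion or more. The shorthand reading does not fit Sections 5 and 7 or the subproject criteria, which use enrolment for a state that precedes completion.

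Second, 10% is conservative and small increases close the gap: 10.7% at 80% completion of 3,500. The reminders, the completion payments and the rule that late completers are still included also make good completion more likely. All of this stands, and it reduces the likely shortfall. It does not make 3,000 enrolled equal to 3,000 completers at the planning values the protocol chose.

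A reader might also take the 300 high-risk participants in Sections 4 and 5 as separate proof that 85.7% completion was built in, since 300 is 10% of 3,000. The documents do not support that. The figure equals 150 / 50% just as well, no passage derives it from 3,000, and it may simply be a target or cap for referral.

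**Conclusion.** The mismatch is real. Section 8 states an enrolment minimum that, at its own 10% and 50%, gives an expected 150 seen only with complete follow-through, and at its upper limit only with at least 85.7%. Over an assumed 70 to 90% completion, the expected number seen is 105 to 135 from 3,000 enrolled and about 122 to 157 from 3,500.

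The effect is confined to Aim 2, which the SAP carries as a secondary endpoint. The Aim 1 total is unaffected down to 66.7% completion of 3,000, subject to the site split. A reader might infer that Aim 2 will miss its target or that the study as a whole is too small. Neither follows: the documents give no completion rate, 10% was chosen to be low, and the power behind the 150 cannot be checked because its inputs are not given. What can be said is that the stated minimum is not sufficient on the plan's own figures, and this should be corrected.

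**What to change.** In Protocol Section 8:

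- Label the 3,000 minimum as participants who complete MeTree, both in the opening paragraph and in the Aim 2 derivation.
- Stop giving 3,000 as a sufficient enrolment minimum.
- State that enrolling up to 3,500 gives 3,000 completers, and so an expected 150 seen, only if at least 85.7% of those enrolled complete.
- Show the expected number seen at 3,000 and 3,500 enrolled for a range of completion rates, for example 70 to 90%, marked as assumptions.

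In Section 2, SA1, give the number to be enrolled and the number to complete separately.

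Report any completion rate observed so far separately, as an observed figure over all enrolled participants. It should not be presented as the planning assumption: completion is the SAP's primary outcome, and an interim result is not a design input. The SAP's Reach population is not the right denominator here, because it is limited to people who clicked the MeTree link.

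The cost is protocol wording only, with no extra enrolment or data. The downside is that the protocol would openly show an expected Aim 2 size below 150 if completion is under 85.7%.

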Hypothesis: MeTree will increase the proportion of high-risk individuals identified.

Statistical interpretation of the hypothesis: P(of high risk) is a function of the intervention

9. Privacy/Confidentiality Issues

The study data live in a REDCap database. *This project will utilize the REDCap platform for data collection and management. Project team members listed as Key Study Personnel with existing electronic health record (EHR) system access rights may also be granted use of REDCap Clinical Data Interoperability Services (CDIS) tools. These tools are designed to enable transfer of relevant study-related data from the Vanderbilt Research Derivative and/or directly from the EHR into REDCap.*

Participant answers to the survey are linked only to a study ID number in a password protected electronic database. Only study staff will have access to the information, and any paper records are kept in a locked drawer in the study manager's desk. Pragmatic studies are considered minimal risk. All data will be gathered and stored using protocols and privacy & security standards that comply with HIPAA and, where applicable, GINA. All patient FHH data will be gathered from patient portal applications and transmitted to and from the algorithm and clinical decision support databases using industry standard encryption protocols, including HTTPS and TLS. The healthcare systems employ additional protections for the data, including detailed audit logs, insulation from direct SQL queries, and detailed version control.

[name]
U01-CA232829-01A1
FOREST

While participant data such as demographics are collected from the VUMC Epic instance, data are delivered by SFTP to the MeTree platform, housed at Duke University, for participants to complete the FHH questionnaire. FHH results will be transmitted by API to a secure REDCap project at VUMC or MMC. *

*This process is approved by the VUMC Architecture Review Board.

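### The protocol's primary endpoint, high-risk designation by the MeTree report against prior chart status, is not estimated or tested in the SAP, which makes MeTree completion primary

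*Protocol*

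**What the plan says.** **Protocol, section 8 (Statistical Considerations).** The endpoint is given as "Primary Endpoint: Participant designated as high risk for cancer". Its two sides are "Assessment pre: chart review (any indicator prior to MeTree, not time-frame dependent" and "Assessment post: MeTree report (measured when the report is generated, independent of amount of follow-up time". The hypothesis is directional: "Hypothesis: MeTree will increase the proportion of high-risk individuals identified". The power graph is described as power for the primary endpoint, and the text adds: "Thus at 10% risk identification and 95% power we estimated that we would need at a minimum 1,000 participants for a single site", with 2,000 for the two sites together.

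The same section names other sources. It says "We will utilize data from the Hereditary Cancer Clinic registry (IRB # 141203" and applies that registry to both the usual-care and the intervention conditions. It also says "The control condition utilizes historical data from the participants prior to their enrollment date in FOREST".

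**SAP.** Section III.1 defines the primary outcome as completion of MeTree, meaning that enough was entered for a risk report to be generated and logged. Section IV.2 reports it as a number and percentage of the Reach population, without inference. The nearest analysis to the protocol's endpoint is Secondary Endpoint 1 (sections III.2.a and IV.3). It compares the presence of a personal- or family-history code in the EHR (Variable 7) up to consent with its presence from consent to study end, by McNemar's test, in the Effectiveness population. Section II.3.f restricts EHR-based analyses to VUMC.

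**The concern.** The two documents name different primary endpoints, and the text supplied does not explain the difference. A reader cannot tell which result the study is to be judged on. The power statement belongs to identification, for which the SAP has no analysis in the protocol's form. The SAP's own primary endpoint has no inference and so makes no use of that power.

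The protocol's question is whether MeTree designates as high risk people whose charts did not already show it. Under the SAP, the report matters only because it exists (completion) and because its recommendation selects the genetic counseling population (section II.3.c). What the report says about risk is never an outcome.

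**Working it through.** **1. The endpoint, side by side.**

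| | Protocol section 8 | SAP Secondary Endpoint 1 |
|---|---|---|
| Rank | Primary | Secondary |
| Pre measure | Chart review, any indicator | EHR personal- or family-history code |
| Pre cut-off | Enrollment in one sentence, MeTree in another | Consent |
| Post measure | MeTree report | EHR personal- or family-history code |
| Post timing | When the report is generated | Consent to study end |
| Depends on follow-up length | No, by its own words | Yes |
| Sites | Sized for two | VUMC only |
| Direction | Increase | Any effect |

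A VUMC participant whom the report flags but whose chart is never coded counts as identified in the first column and not identified in the second. Secondary Endpoint 1 therefore measures documentation of risk in the EHR.

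**2. Count of identification tests in the SAP.**
- IV.3: Variable 7, Effectiveness population: 1
- IV.5: Variable 7, Reach population: 1
- IV.6: Variable 1, both populations: 2
- IV.7: Variable 2, both populations: 2

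The total is 1 + 1 + 2 + 2 = 6. None uses the report's high-risk result.

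**3. What the protocol's sample sizes refer to.** The minimum of 3,000 reproduces exactly, and it comes from Aim 2: 150 high-risk patients seen, 10% identified, 50% follow-up, so 150 / (0.10 × 0.50) = 3,000. The identification endpoint carries the 1,000 and 2,000 figures.

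The 1,000 can be neither confirmed nor refuted. The readable text gives no comparator or discordant-pair rate, and the graph is not shown. For a paired test, with p10 the proportion newly identified, p01 the reverse discordance and two-sided 0.05:

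n = [1.96 √(p10 + p01) + 1.645 √(p10 + p01 − (p10 − p01)²)]² / (p10 − p01)²

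At p10 = 10% and 95% power, and with p01 assumed:
- p01 = 0%: 124 pairs
- p01 = 5%: [1.96 √0.15 + 1.645 √0.1475]² / 0.05² gives 774 pairs
- p01 = 6%: 1,294 pairs
- p01 = 7.5%: 3,633 pairs

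The figure of 1,000 is thus attainable, but only for an unstated reverse discordance between 5% and 6% under this formula. The protocol needs to say which analysis the figure was computed for.

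**4. Precision of the estimate that is not planned.** Clopper-Pearson 95% intervals at the protocol's 10%, with the number of completers assumed because neither document gives it:
- 100/1,000: 8.2–12.0%
- 200/2,000: 8.7–11.4%
- 300/3,000: 8.9–11.1%

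These show what an added estimate could deliver. They do not measure bias in any existing analysis.

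**5. The protocol's own sources.** Section 8 gives chart review (pre) and the MeTree report (post), and it also uses the clinic registry for both conditions. So neither side has a single stated source. The history is cut both at enrollment and at MeTree; the SAP's consent cut-off fits only the first.

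**The case against.** **Secondary Endpoint 1 already covers identification.** In part it does. A reader might infer that the SAP has dropped the identification hypothesis, and that is not so: it is tested, as a secondary endpoint, in MeTree completers. The protocol's use of the registry for both conditions also makes a records-based post measure less foreign to the protocol than its endpoint definition suggests. What remains is that the stated post assessment is the report at generation, independent of follow-up, and no SAP analysis uses it.

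**Completion is a proper implementation endpoint.** It is, and it traces to the protocol's first specific aim. The point is not that completion must go, but that one document calls it primary and the other does not.

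**The missing test should not simply be prescribed.** This objection stands. The supplied text does not define high-risk status on the report: protocol section 8 speaks of high risk for cancer, and section 5 says "in Aim 2 participants who are identified as at high genetic risk (n=300) will be contacted by the study nurse". A McNemar test of EHR codes against the report would compare two instruments with different thresholds. If the codes are broader than the report's rule, MeTree could appear to lower identification through definition alone. The fix therefore limits when that test is used.

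**The protocol paper may explain the change.** The SAP cites it for the populations; it was not available. Even if it does, the protocol and the SAP would still name different primary endpoints.

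**Conclusion.** The contradiction is in the text and must be resolved. The protocol's primary endpoint has no estimate and no test in the SAP (0 of 6 identification tests use the report's result), and the 1,000 and 2,000 power figures belong to no planned analysis of that endpoint.

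Three stronger readings are not supported:
- **The primary endpoint was changed after results were seen.** The documents do not show when the choice was made or whether outcome data had been examined. Equally, they do not show that the gap can still be closed before analysis.
- **The enrollment target loses its basis.** The 3,000 minimum rests on Aim 2, not on this endpoint.
- **The study is underpowered for identification.** The inputs needed to judge that are not in the readable text. At 10%, even 1,000 completers would give an interval of about ±2 points.

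The conclusion rests on the wording of the two documents. Only the precision figures depend on an assumption, the number of completers.

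**What to change.** 1. **Align the primary endpoint.** Name the same one in both documents, or document and justify the change and its timing. State which analysis the 1,000 and 2,000 figures refer to, and that the 3,000 minimum comes from Aim 2. Reconcile the protocol's sources (chart review, registry, report) and its two cut-offs.
2. **Add one SAP estimate of the protocol's endpoint.**
   - Define high-risk status on the report, for example as a hereditary-cancer genetic counseling recommendation on the first generated report. The choice of report matters because protocol section 5 allows updated reports that may alter that status.
   - Report the proportion designated high risk with an exact 95% CI, by site where report data exist. Protocol section 9 sends family-history results to REDCap at VUMC or Meharry, so this part need not be VUMC-only.
   - In VUMC completers, cross-tabulate report status with pre-MeTree status. Show both discordant cells, and the proportion newly identified with an exact 95% CI.
   - Use McNemar's test only if the pre status is the protocol's chart review or another measure of the same high-risk definition. If only EHR codes are available, use Variable 7 as a declared proxy, cut at consent, and keep the table descriptive.
   - Label the analysis post hoc if outcome data have already been seen.
3. **Describe Secondary Endpoint 1** as EHR documentation of risk before and after consent.

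The cost is SAP wording and one extra table. SAP section III.1 says the report is logged in the study database, so the proxy version needs no new data collection provided the risk result is stored with it. Chart abstraction is needed only if the protocol's chart review is used and was not already done.
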